10.4 STATISTICAL ANALYSES

10.4.1 General Approach

Patients who are in the safety evaluation will have the number of patients with a DLT determined. Patients who are in the efficacy evaluation and patients from the safety run-in administered the M7824 and M9241 in combination with SBRT dose used in the phase II part of the study will have the fraction of clinical responses determined.

10.4.2 Analysis of the primary endpoints

For the patients in the dose de-escalation portion, the safety and tolerability and the recommended phase 2 dose (RP2D) of M7824 and M9241 in combination with SBRT as neoadjuvant / perioperative treatment in subjects with pancreas cancer will be evaluated by reporting the number, severity, and duration of treatment-related AEs for the combination treatment of M7824 and M9241 administered in combination with a 5-day course of SBRT according to CTCAE v5.0 . The rate of completion of neoadjuvant SBRT courses when given with M7824 and M9241 will be reported as well using descriptive statistics.

Patients who are in the efficacy evaluation will have the fraction objective responses measured by RECIST1.1 determined by dividing the number of patients with an objective response by the number of evaluable patients who are treated at the MTD and reported along with two sided 80% and 95% confidence intervals.

10.4.3 Analysis of the secondary endpoints

The secondary endpoints will be analyzed as follows:

- Overall survival in patients after completion of SBRT in combination with M9241 and M7824 and Progression-Free Survival (PFS) of all patients and PFS of patients who did not undergo surgical resection (expressed as median PFS). Overall survival and PFS will be determined in all patients treated at the MTD of M7824 and M9241 in combination with SBRT, as well as patients who did not undergo surgery, using Kaplan-Meier curves.
- Fraction of patients with LAPC who are able to undergo surgical resection after M7824 and M9241 in combination with SBRT treatment. This will be reported along with a 95% confidence interval on the fraction.

- Time-to-recurrence in patients who underwent surgical resection will be measured as time from surgical resection to disease recurrence (expressed in months). Time-to-recurrence in patients will be calculated via Kaplan-Meier curves. Any comparisons with published results will be interpreted as being exploratory.
- Rate of complete pathologic response will be measured as fraction of patients who had a complete pathologic response of all patients who underwent surgery. This will be reported along with a 95% confidence interval.

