1 INTRODUCTION

1.1 STUDY OBJECTIVES:

1.1.1 Primary Objectives:

- To determine the safety and tolerability and the recommended phase 2 dose (RP2D) of M7824 and M9241 in combination with SBRT as neoadjuvant / perioperative treatment in subjects with pancreas cancer.
- To determine a preliminary estimate of efficacy as best overall response (BOR) according to RECIST 1.1 of M7824 and M9241 in combination with SBRT as neoadjuvant / perioperative treatment in subjects with locally advanced pancreas cancer.

1.1.2 Secondary Objectives:

- To assess overall survival (OS) in patients after completion of RT in combination with M9241 and M7824.
- To assess progression-free survival (PFS) for all participants.
- To assess progression-free survival (PFS) for participants who did not undergo surgical resection.
- To determine fraction of patients with LAPC who are able to undergo surgical resection after M7824 and M9241 in combination with SBRT treatment.
- For patients who underwent surgical resection after M7824 and M9241 in combination with SBRT treatment:
 - To determine time-to-recurrence of the disease
 - To determine complete pathological response rate(s)

1.1.3 Exploratory Objectives:

- To determine ADA profile of M7824 in combination with M9241.

- To determine the PK of M7824 in combination with M9241.
- To evaluate serum cytokines and tumor necrosis factor (TNF) levels pre-treatment and on-treatment.
- To correlate the tumoral immune infiltrate via IHC with clinical outcome.
- To evaluate impact of genomic profile of advanced pancreatic cancers on clinical response to M7824 and M9241 in combination with SBRT.
- To correlate circulating free tumor DNA (ctDNA) levels with clinical course of pancreatic cancer patients treated with M7824 and M9241 in combination with SBRT.
- To measure subjective Health-related Quality of Life (HRQoL) affecting disease-specific symptoms and treatment-related concerns pre-treatment and on-study and compare HRQoL scores with historical controls of other Quality of Life (QoL) interventions in advanced pancreas cancer patients.
- To evaluate the impact of M7824 in combination with M9241 on tumoral perfusion measured by perfusion-weight Dynamic Contrast-enhanced (DCE) Magnetic Resonance Imaging (DCE-MRI).

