The primary goal of neoadjuvant therapy in LAPC is, among tumor control and extension of survival, the conversion to resectable disease achieving a R0 resection.[4] Some series have reported for patients with initially borderline resectable pancreas cancer who after neoadjuvant therapy were able to undergo a margin-negative surgical resection of their tumor similar outcomes like for patients with initially resectable disease.[4, 6, 8, 9] However, even after multimodality therapy that includes surgical resection, 5-year overall survival only reached 25 – 30% with an ongoing risk of systemic and locoregional disease recurrence speaking to the systemic nature of the disease and making pancreas cancer, even in its early stages, a near incurable condition.[4, 7, 9]

Patients unable to undergo margin-negative resection have a poor outcome frequently similar to patients with stage IV disease and have poor quality of life indices due to challenging palliation of gastric outlet, biliary duct obstruction, or neuropathic pain due to local tumor progression.[4] Currently used neoadjuvant RT treatment regimens result in only about 40 – 60% of patients with borderline resectable pancreas cancer to undergo surgical resection and in unresectable LAPC patient conversion are even lower, with only 7% - 19% being able to undergo resection which is increased to 29% with the use of the most involved and toxic combination of triple FOLFIRINOX chemotherapy in combination with RT in highly selected patients.[5, 6, 10] [Figure 2](#) shows the flow diagram and outcome differences between all locally advanced pancreas cancer patients (intent-to-treat), outcome of patients who were able to undergo surgical resection, and patients who could not undergo surgery of one of the first sentinel series on the use of neoadjuvant therapy using gemcitabine-based chemoradiation therapy.[9]

[figure not shown]

Figure 2: MDACC experience of preoperative gemcitabine-based chemoradiation (EBRT) for patients with potentially resectable (borderline) adenocarcinoma of the pancreatic head. Flowchart of all 86 patients on the left, survival curve for all 86 patients and survival curves for the patients who underwent pancreaticoduodenectomy (PD; n=64) versus those who did not undergo PD (n=22). The median overall survival for all patients (intent-to-treat) was 22.7 months, for the resected patients 34 months, and for patients not taken to surgery 7 months.[9]

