At Cycle 3 Day 15 (+/- 7 days) patient will undergo imaging and every 2 Cycles (+/-5 days) thereafter.

[figure not shown]
If during the treatment patient's tumors become resectable per standard of care, M7824 and/or M9241 will be stopped at least 5 days prior to the scheduled date of surgery. Surgery is not part of this protocol and will be done as standard of care procedure with enrollment of patient to another surgical protocol in NIH or at home institution.

If surgical exploration does not result in a successful removal of the tumor, patient will be able to return to treatment following recovery from surgery (See section 3.5.3). If tumor removed successfully, patient will be taken off protocol treatment.

Schema 1: Phase IA.

Schema 2: Phase IB

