10.1.2 Secondary endpoints

- Overall survival in patients after completion of SBRT in combination with M9241 and M7824.
- Progression-free survival of all patients and PFS of patients who did not undergo surgical resection (expressed as median PFS).
- Fraction of patients with LAPC who can undergo surgical resection after M7824 and M9241 in combination with SBRT treatment.
- Time-to-recurrence in patients who underwent surgical resection will be measured as time from surgical resection to disease recurrence (expressed in months).
- Rate of complete pathologic response will be measured as fraction of patients who had a complete pathologic response of all patients who underwent surgery.

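### The PFS and OS curves in patients never operated on select by a later event, so their medians understate outcome without resection even if surgery does nothing

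*Combined protocol and SAP*

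**What the plan says.** Section 1.1.2 lists as a secondary objective "To assess progression-free survival (PFS) for participants who did not undergo surgical resection". Section 10.1.2 makes it an endpoint, "PFS of patients who did not undergo surgical resection (expressed as median PFS"). Section 10.4.3 says that OS and PFS will be determined in all patients treated at the MTD with SBRT, "as well as patients who did not undergo surgery, using Kaplan-Meier curves". OS in the non-surgery group appears only in 10.4.3; the objectives and endpoints name PFS alone.

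Surgery is not assigned at entry. Under section 3.1 it arises "If during the treatment patient's tumors become resectable per standard of care", and section 3.5.3 repeats this. The first scheduled on-treatment look is also in 3.1: "At Cycle 3 Day 15 (+/- 7 days) patient will undergo imaging".

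The plan gives no landmark, no censoring at surgery and no time-dependent handling of surgery. It states no time origin for PFS, and OS is worded as survival after completion of SBRT. The only interpretive caution in 10.4.3 concerns comparing time-to-recurrence with published results. That section also refers to surgical resection in one sentence and to surgery in the next. Patients explored but not resected, a category that section 3.5.3 recognises, are classified differently under the two wordings.

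**The concern.** A patient is counted as never operated on because of what happens during follow-up. Anyone who progresses or dies before surgery could be scheduled is placed in that group. Anyone who does well for long enough may be moved out. The group is enriched for early failures by construction, so its Kaplan-Meier curve drops faster than the curve for the same patients had none been resected.

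A reported secondary median is at stake. A reader is likely to use it as the outcome of the regimen without surgery, to compare it with the all-patient median as if the gap were due to surgery, or to set it beside historical medians for unresected disease. The protocol cites about 1 year for OS after SBRT (section 1.2.7) and about 9 months (section 12.4.3). Section 1.2.1 already presents a split of this kind from an earlier series: "for the resected patients 34 months, and for patients not taken to surgery 7 months".

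**Working it through.** **The plan's own figure.** The documents give no target, power or expected value for PFS or OS. The nearest checkable figure is the Simon stopping probability under a 10% response rate: 0.9^16 + 16 × 0.1 × 0.9^15 = 0.515, as stated. That rule uses response only, so nothing below affects it.

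**Inputs from the documents.**
- First scheduled scan: Cycle 3 Day 15 is day 28 + 28 + 15 = 71, about 2.3 months from Cycle 1 Day 1.
- Resection fraction in unresectable disease (section 1.2.1): "with only 7% - 19% being able to undergo resection which is increased to 29" per cent.
- Resection fraction in borderline disease (section 1.2.1): "40 – 60% of patients with borderline resectable pancreas cancer to undergo surgical resection". Section 2.1.1 admits both groups to Cohorts 2 and 3.

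**Assumptions.** Event time T is exponential with median 6, 9 or 12 months. A share q of patients are surgery candidates, with surgery planned uniformly between 3 and 6 months, independently of T. They are resected only if still event-free, and surgery does not change T. The documents supply neither the distribution nor the surgery timing.

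**Formulas.** Let λ = ln 2 / median and S(t) = exp(−λt).
- Resected fraction: r = q × [S(3) − S(6)] / (3λ).
- Never-resected survival for t ≥ 6: (1 − q) S(t) / (1 − r).
- Never-resected survival for 3 ≤ t < 6: {S(t) − q [S(t)(t − 3)/3 + (S(t) − S(6))/(3λ)]} / (1 − r).

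**True median 9.** λ = 0.0770, S(3) = 0.794 and S(6) = 0.630, so [S(3) − S(6)] / (3λ) = 0.709 and q = r / 0.709. The never-resected median is where its survival equals 0.5.

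| Resected r | q | (1 − q)/(1 − r) | S(t) needed | Median |
|---|---|---|---|---|
| 7% | 0.099 | 0.969 | 0.516 | 8.6 |
| 19% | 0.268 | 0.904 | 0.553 | 7.7 |
| 29% | 0.409 | 0.832 | 0.601 | 6.6 |
| 33% | 0.466 | 0.798 | 0.627 | 6.1 |

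At 50% resected (q = 0.706) the median lies below 6 months, so the third formula applies. At t = 3.81, S(t) = 0.746, the square bracket is 0.201 + 0.501 = 0.702, and (0.746 − 0.706 × 0.702)/0.5 = 0.50. The median is 3.8.

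**Simulation, 2,000,000 patients per scenario.** It agrees with these values and gives the other true medians:

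| True median | 7% | 19% | 29% | 33% | 50% |
|---|---|---|---|---|---|
| 6 | 5.6 | 4.6 | 3.9 | 3.6 | 2.5 |
| 9 | 8.6 | 7.7 | 6.6 | 6.1 | 3.8 |
| 12 | 11.6 | 10.8 | 9.8 | 9.3 | 5.9 |

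In the same model, ending unresected follow-up at surgery returns the true median at every fraction. With true median 9 and 29% resected, a 6-month landmark gives a residual median of 9.0 in all, resected and non-resected patients alike.

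**At trial size.** With 25 patients, true median 9 and about 29% resected, the never-resected sample median averages 7.1 against 9.3 for all patients, and is the lower of the two in 88% of trials.

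**The cited series.** With an OS median of 22.7 months, 64/86 = 74% resected and no surgery effect, the same model gives a never-resected median of 9.7 (surgery at 2 to 5 months) or 5.1 (3 to 6 months), and a resected median of 26 to 27. The series reported 7 and 34.

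**The case against.** The strongest reply is that the objective is descriptive. It asks for PFS in participants who were not resected, and the planned curve answers that correctly. No test of surgery against no surgery is planned. Resected patients get a different measure, time-to-recurrence counted from surgery. All-patient OS and PFS come first in 10.4.3. All of this stands, so the stronger reading that the endpoint is invalid, or that the plan sets out to estimate a surgery effect, is not supported. The fault lies in an interpretation that the plan invites and does not warn against.

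A reader might also infer that the curves run from treatment start. The documents do not say so. The mechanism does not depend on it: SBRT starts at Day 17 (up to 5 days later) and takes five business days, so even completion of SBRT, at about Day 28, precedes the first scheduled scan. Any origin before surgery has the same problem.

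The sizes rest on assumed timing and distribution. At the low end of the protocol's resection range the shift is about half a month. With 25 patients and a true median of 8, the sampling standard deviation of the non-surgery median is about 2.5 months. The shift there (8.0 to 7.1, 6.2 or 5.0 at about 14%, 24% or 34% resected) is then roughly 0.4 to 1.2 standard deviations. That is fair, but noise has no preferred direction and this shift does.

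Finally, the cited 34 against 7 months is OS in a potentially resectable pancreatic-head series with 74% resected, and may include a real surgery effect. The check shows only that selection alone can give a non-surgery median of that order. It does not show that surgery had no effect there.

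**Conclusion.** The concern holds as a matter of interpretation and is cheap to correct. The never-operated median is shorter than the outcome without resection in every scenario examined. With a true median of 9 months the shortfall is about 0.4 months at 7% resected, 1.3 at 19%, 2.4 at 29% and 5.2 at 50%. These sizes assume exponential event times, surgery at 3 to 6 months and no link between prognosis and surgery. The direction needs only that resection requires remaining event-free.

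A reader might infer that a time-dependent analysis restores the true median exactly. It does so only if resection is unrelated to prognosis. Here patients are resected because the tumor became resectable, which makes that unlikely. An illustrative run with a gamma frailty linking prognosis to surgery left 0.7 to 1.1 months of error, against 3.1 to 3.6 months for the analysis as planned. The documents do not fix the frailty strength, so those figures indicate order of size only.

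The go/no-go decision on response and the all-patient PFS and OS curves are unaffected.

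**What to change.** Amend section 10.4.3, and align 1.1.2 and 10.1.2 with it.

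- Keep all-patient PFS and OS as the main results.
- Replace the non-surgery curves with an analysis that treats resection as time-dependent (Simon-Makuch). Each patient at the RP2D contributes to the unresected curve from one stated time origin until the date of actual tumor resection, and to the resected curve only afterwards. Patients explored without resection stay in the unresected curve; changing status on the day of any operation would misplace them. Say which of the categories in section 3.5.3 count as resection.
- Alternatively, use a landmark among patients event-free at a fixed scheduled scan.
- Use surgical resection consistently in place of surgery.
- State the time origins for PFS and OS, and reconcile them with the wording about completion of SBRT.
- Label the result descriptive, noting that selection by prognosis remains.

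The cost is wording and a few lines of code, with no added patients or visits. Section 6.1.3 lists counts of explorations and resections, not dates, but time-to-recurrence already requires the resection date. The downsides are a curve that is slightly harder to explain and the residual selection described in the verdict.

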3.5.3 Treatment pauses for surgery

Surgery is not part of this protocol and will be done as standard of care procedure with enrollment of patient to another surgical protocol at the NIH Clinical Center or at home institution.

If during the treatment patient's tumors become resectable per standard of care, M7824 and/or M9241 will be stopped at least 5 days prior to the scheduled date of surgery.

If surgery performed outside NIH, we will ask patients to provide the outside surgical pathology report for determination of resection status (R0, R1, R2) and tumor sample from this surgery for research.

If surgical exploration does not result in a successful removal of the tumor as defined below:

- R0: closest tumor ≥ 1 mm from surgical resection margin
- R1: tumor within < 1 mm of surgical resection margin

- R2: involvement of surgical resection margin with tumor (incomplete tumor clearance)
- “open and close”

treatment with M7824 and M9241 will resume 6-8 weeks after surgery when patient recovers. SBRT will not be repeated.

If surgical exploration results in a successful removal of the tumor, patient will be taken off study treatment.

Before post-surgery re-treatment with M7824 and M9241, Day 1 the following tests and examinations must be performed to evaluate safety of re-treatment and estimate baseline for tumor evaluations:

Within 28 days:

- CT/MRI of chest, abdomen and pelvis;
- Research Quality of Life assessment (subject-reported outcomes / symptom severity assessments the 4th version of the ‘Functional Assessment of Cancer Therapy with the hepatobiliary and pancreatic specific module ([Appendix C](#)). (For English speaking subjects only)

Within 3 days:

- Physical examination, including weight, vital signs, EKG, and ECOG performance status;
- Adverse event and concomitant medications;
- Laboratory evaluation:
 - Hematological profile: CBC with differential and platelet count;
 - Biochemical profile: Acute care panel (that includes sodium, potassium, BUN, creatinine), Hepatic panel (that includes AST, ALT, total bilirubin), Mineral panel (that includes calcium, phosphorus, albumin, and magnesium), and uric acid;
 - CEA, CA19-9, CA-125
 - T4, TSH
 - Amylase/ lipase
 - Serum or urine pregnancy test for female participants of childbearing age (in the absence of prior hysterectomy)
 - Urinalysis.

Research blood will not be collected during post-surgery treatment

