6.1.3 Concomitant Medications and Therapies

All concomitant medications taken by the subject during the trial, from the date of signature of informed consent are to be recorded in the appropriate section of the eCRF, noting the name, dose, duration and indication of each drug. Nondrug interventions should also be recorded in the eCRF.

The following outcome criteria will be captured if surgery performed while patient is on study:

- Number of patients explored
- Number of patients to undergo resection
- Number of R0, R1, and R2 resection

End of study procedures: Data will be stored according to HHS, FDA regulations and NIH Intramural Records Retention Schedule as applicable.

Loss or destruction of data: Should we become aware that a major breach in our plan to protect subject confidentiality and trial data has occurred, this will be reported expeditiously per requirements in section [7.2.1](#).

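### The secondary surgical endpoints use inconsistent patient sets: pCR is divided by operated rather than resected patients, time-to-recurrence admits R2 cases, and no R0 rate is planned

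*Combined protocol and SAP*

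**What the plan says.** **Resection.** The objective (1.1.2), endpoint (10.1.2) and analysis (10.4.3) agree. The quantity is the "Fraction of patients with LAPC who are able to undergo surgical resection after M7824 and M9241 in combination with SBRT treatment", reported with a 95% confidence interval. Margin is not part of the definition, and no analysis population is named for the denominator.

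**pCR.** Section 1.1.2 places pCR and time-to-recurrence together under patients who had a resection. Sections 10.1.2 and 10.4.3 instead define pCR as the "fraction of patients who had a complete pathologic response of all patients who underwent surgery".

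**Time-to-recurrence.** Section 10.4.3 measures it from resection to recurrence by Kaplan-Meier in all resected patients, whatever the margin. It does not say how death without recurrence is handled.

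**Margin status.** Section 1.2.1 describes the main goal of neoadjuvant therapy in LAPC as "the conversion to resectable disease achieving a R0 resection", and adds: "Patients unable to undergo margin-negative resection have a poor outcome frequently similar to patients with stage IV disease". For surgery outside the NIH, 3.5.3 says "we will ask patients to provide the outside surgical pathology report for determination of resection status (R0, R1, R2"). Section 6.1.3 lists "Number of patients explored", the number resected and "Number of R0, R1, and R2 resection" as separate items. No objective, endpoint or analysis uses R0.

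**Surgical outcome classes.** Section 3.5.3 lists R0, R1, R2 and open-and-close together under exploration that failed to remove the tumor. It defines the third as "R2: involvement of surgical resection margin with tumor (incomplete tumor clearance").

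**The concern.** Three things do not fit together. First, an open-and-close patient has had surgery but has no resected specimen in which a pCR could be found. The pCR rate as written in 10.4.3 is therefore diluted by failed explorations and is not the quantity named in the objective. Second, an R2 patient has residual tumor on the day of surgery, so the recurrence clock starts in someone who was never free of disease. Third, the protocol says why a clear margin matters and collects the margin, but plans to report only a rate in which R2 counts the same as R0.

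What is at stake is how the surgical results can be read. The pCR and time-to-recurrence figures could differ between two analysts who both follow the text, and the resection rate could be taken for an R0 conversion rate. If an R0 rate is left until margins are known in about 25 patients, its denominator and classification remain open to choice.

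**Working it through.** **1. The plan's own figure, and whether it depends on these endpoints.** Section 10.2 gives p0 = 0.10, p1 = 0.30, stop at 0-1 of 16, and success at 5 or more of 25.

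P(early stop | 0.10) = 0.9^16 + 16 × 0.1 × 0.9^15 = 0.1853 + 0.3294 = 0.5147, against the stated 51.5%.

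The exact two-stage calculation gives type I error 0.0951 (limit 0.10) and power 0.9030 (limit 0.90). The design reproduces. It uses RECIST response only; no threshold or power is stated for resection, pCR or recurrence.

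**2. Sets side by side.**

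| Quantity | 1.1.2 | 10.1.2 | 10.4.3 |
|---|---|---|---|
| Resection fraction | LAPC, any margin | LAPC, any margin | LAPC, any margin; population not named |
| pCR | resected | operated | operated |
| Time-to-recurrence | resected | resected | resected, R2 not excluded |
| PFS subgroup | not resected | not resected | not resected, then not operated |
| R0 fraction | none | none | none |

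The operated and resected sets differ by the open-and-close patients, whom 3.5.3 names. Section 6.1.3 counts explored and resected patients separately.

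**3. Size for pCR (assumed counts: 8 resected, 10 operated, 25 treated).** Rate = x/n. The Clopper-Pearson 95% limits are the Beta(x, n−x+1) quantile at 0.025 and the Beta(x+1, n−x) quantile at 0.975.

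| pCR events | Resected | Operated | All treated |
|---|---|---|---|
| 1 | 1/8 = 12.5% (0.3-52.7) | 1/10 = 10.0% (0.3-44.5) | 1/25 = 4.0% |
| 2 | 2/8 = 25.0% (3.2-65.1) | 2/10 = 20.0% (2.5-55.6) | 2/25 = 8.0% |

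The operated denominator can only lower the rate, here by 2.5 to 5 points.

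**4. Size for R0 (assumed: 10 of 25 resected).** Any resection is 10/25 = 40.0% (21.1-61.3).

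| Assumed R0 share | R0 rate (95% CI) | Gap |
|---|---|---|
| 97% | 10/25 = 40.0% (21.1-61.3) | 0 points |
| 80% | 8/25 = 32.0% (14.9-53.5) | 8 points |
| 70% | 7/25 = 28.0% (12.1-49.4) | 12 points |
| 50% | 5/25 = 20.0% (6.8-40.7) | 20 points |

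The only R0 frequency in the documents is 31/32 = 96.9%, in a cited borderline-resectable series (1.2.7). The 97% row corresponds to it.

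**5. Time-to-recurrence.** For an R2 patient the analyst must either place an event at time zero or wait for progression, which is not recurrence; 10.4.3 does not choose. If 2 of 8 resected patients were R2 (assumed), 2/8 = 25% of the curve would come from patients never cleared of tumor.

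**6. Margin classes.** Tumor exactly at the margin (0 mm) satisfies the R1 distance criterion (under 1 mm) and also the R2 criterion of margin involvement. The overlap cannot change an R0 rate, but it decides who leaves the time-to-recurrence set once R2 is excluded.

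**The case against.** The strongest reply is that nothing decisive rests on these endpoints. They are secondary and descriptive, without hypothesis or threshold, and 10.4.3 already labels comparisons of time-to-recurrence with published results as exploratory. A reader might infer that the trial's success is misstated. The documents do not support that: the only success rule is the RECIST response rule in 10.2, and a fraction labelled as surgical resection is accurate for what it counts.

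A reader might also infer that R0 is the trial's objective and should replace any resection. Section 1.2.1 states a goal of neoadjuvant therapy in LAPC generally. The benchmarks given there are resection rates without a margin condition: 40-60% in borderline disease, 7-19% in unresectable disease, and 29% with FOLFIRINOX plus RT. Any resection is the comparable measure, so it should stay.

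On pCR, the wording may simply be loose, since the PFS bullet in 10.4.3 also moves between resection and surgery. Read literally, the wording understates pCR, so it cannot flatter the regimen. The 31/32 figure suggests that the R0 gap could be negligible.

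Much of this stands and limits the point. It does not remove it. Loose wording still allows two different pCR rates. The 31/32 series covers borderline patients and gave 35 Gy to the area of vessel involvement, whereas Cohorts 2 and 3 also admit unresectable disease (2.1.1), so a near-zero gap cannot be presumed. R2 handling in time-to-recurrence is unaddressed on any reading.

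**Conclusion.** The point holds as a set of inconsistencies in the secondary surgical analyses. The pCR denominator in 10.1.2 and 10.4.3 contradicts the objective in 1.1.2. Time-to-recurrence includes patients to whom the term does not apply in its usual sense. Margin status is collected but no R0 rate is analysed.

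On assumed counts, pCR shifts by 2.5 to 5 points (8 resected against 10 operated), and any resection exceeds R0 by 0 to 20 points (10/25 resected, R0 share 97% down to 50%). These sizes rest on invented counts; the documents give no expected resection, exploration or R0 numbers for this trial. All the intervals are wide.

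The conclusion goes no further. The phase II go/no-go rule is untouched, and the text does not show an inflated pCR rate or a misreported resection rate.

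**What to change.** In 10.1.2 and 10.4.3:

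- **pCR:** use resected patients as the denominator, as in 1.1.2, and also report pCR over all LAPC patients treated at the RP2D.
- **Time-to-recurrence:** restrict it to R0/R1 patients, list R2 patients separately, and state how death without recurrence is handled. Counting death as an event is a legitimate choice, but it makes the endpoint recurrence-free survival and it should then be named so.
- **Resection:** keep any resection as the endpoint. Beside it, report R0 resections over all LAPC patients treated at the RP2D, with a 95% confidence interval.
- **Margins:** for this analysis, define R1 and R2 so that they are mutually exclusive.

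Separately, the list in 3.5.3 puts R0 with R1, R2 and open-and-close under unsuccessful removal, while 3.1, 3.5.3 and 3.11.1 take successfully operated patients off treatment. Read literally, no margin class is left for a successful removal. These passages must be reconciled by the sponsor.

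The cost is a protocol and SAP wording amendment with IRB approval, a smaller time-to-recurrence set, and an R0 rate that may look less favorable than the any-resection rate. No patients or data items are added, although margin status after outside surgery depends on patients supplying the pathology report.
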